Table 7:	Sensitive CYP3A4 Substrates with Narrow Therapeutic Index	37
Table 8:	Examples of Moderate and Strong CYP3A4 Inducers	37
Table 9:	Grading for Adverse Events Not Covered in the NCI CTCAE	48
Table 10:	Reporting of Medication Errors	55

LIST OF FIGURES

Figure 1:	Study	Schema	26
0	Sectore 12		

LIST OF ABBREVIATIONS

Abbreviation	Definition
ACS	acute chest syndrome
ADL	activities of daily living
AE	adverse event
ALK	alkaline phosphatase
ALT	alanine aminotransferase
AST	aspartate transferase
BP	blood pressure
CCI	
CL	clearance
COVID-19	coronavirus disease of 2019
CRO	contract research organization
CYP	cytochrome P450
DILI	drug-induced liver injury
DSMB	Data and Safety Monitoring Board
EC	Ethics Committee
ECG	electrocardiogram
eCRF	electronic case report form
EDB	exposure during breastfeeding
EDP	exposure during pregnancy
EDC	electronic data capture
EOS	end of study
EOT	end of treatment
CCI	
EOS	end of study
ETD	early treatment discontinuation
FDA	Food and Drug Administration
FEMA	Flavor and Extract Manufacturers Association of the United States
GBT	Global Blood Therapeutics, Inc.
GCP	Good Clinical Practice
GRAS	Generally Recognized as Safe
Hb	hemoglobin
HbF	fetal hemoglobin
Hb-O ₂	hemoglobin-oxygen
HbS	sickle hemoglobin

Abbreviation	Definition
HbS-O ₂	sickle hemoglobin-oxygen
Hct	hematocrit
HIV	human immunodeficiency virus
HU	hydroxyurea
IB	Investigator's Brochure
ICF	informed consent form
ICH	International Council for Harmonisation
IID	Inactive Ingredient Database
INR	international normalized ratio
IPF	idiopathic pulmonary fibrosis
IRB	Institutional Review Board
ITT	Intent to Treat
IXRS	Interactive Response System
LC/MS/MS	liquid chromatography mass spectrometry
LDH	lactate dehydrogenase
LFT	liver function test
MMRM	mixed model for repeated measures
NCI CTCAE	National Cancer Institute Common Terminology Criteria for Adverse Events
NIH	National Institutes of Health
PD	pharmacodynamic(s)
PE	physical examination
Ph Eur	European Pharmacopoeia
РК	pharmacokinetic(s)
PPK	population pharmacokinetic(s)
PT	prothrombin time
O ₂	oxygen
RBC	red blood cell
RSI	Reference Safety Information
SAE	serious adverse event
SAP	statistical analysis plan
SCA	sickle cell anemia
SCD	sickle cell disease
SRSD	Single Reference Safety Document
SUSAR	Suspected Unexpected Serious Adverse Reactions
TAMMV	time-averaged mean of the maximum
TCD	transcranial Doppler

Abbreviation	Definition	
TEAE	treatment-emergent adverse event	
TIA	transient ischemic attack	
ULN	upper limit of normal	
US	United States	
USA	United States of America	
USPI	United States Prescription Information	
VOC	vaso-occlusive crisis	
WBC	white blood cell	

STUDY ADMINISTRATIVE STRUCTURE

Sponsor:

Global Blood Therapeutics, Inc.

[name] USA [contact] [contact]

Sponsor's Responsible Medical Officer/Medical Monitor and Study Director: The contact information is documented in the study contact list located in the Study Binder

PROTOCOL SYNOPSIS

Study Number	r GBT440-032, Amendment 4		
Study Title	A Phase 3, Randomized, Double-Blind, Placebo-Controlled Study of Voxelotor (GBT440) in Pediatric Participants with Sickle Cell Disease (HOPE Kids 2)		
Investigational Product	Voxelotor as 500 mg tablets or as 300, 400, 600, and 900 mg powder for oral suspension (packaged in stick pack pouches) or as 100 and 300 mg dispersible tablets Matching placebo		
Sponsor	Global Blood Therapeutics, Inc.; a wholly owned subsidiary of Pfizer Inc. [name] United States of America		
Number of Clinical Sites	The study will be conducted at approximately 50 international clinical sites.		
Number of Study Participants	Approximately 224 participants with sickle cell disease (SCD), aged ≥ 2 to < 15 years.		
Treatment	Participants will be randomized in a 1:1 ratio to receive voxelotor or placebo. All participants younger than 12 years of age and randomized to voxelotor will receive a dose based on their body weight to provide exposure corresponding to the adult dose of 1500 mg/day. Participants 12 years or older will take 1500 mg/day. Participants will receive study drug as a tablet dosage form or powder for oral suspension dosage form (packaged in stick pack pouches). If powder for oral suspension is not available, dispersible tablets will be used.		
	Voxelotor, in all dosage forms, may be taken with or without food. Voxelotor tablets should be swallowed whole. The powder for oral suspension should be mixed with liquid. Likewise, voxelotor dispersible tablets should be dispersed in liquid. Details regarding preparation of voxelotor for administration are provided in the Pharmacy Manual (provided separately).		
	The participant's weight at screening will be used to determine their initial treatment dose. Dosing should be adjusted if the participant's weight increases or decreases at any clinic visit. The participant's weight will be measured and dose adjustments will be made as needed, as outlined in the Pharmacy Manual.		
Objectives	Primary Objective: The primary objective is to evaluate the effect of voxelotor compared to placebo on the transcranial Doppler (TCD) time-averaged mean of the maximum velocity (TAMMV) arterial cerebral blood flow at 24 weeks in SCD participants ≥ 2 to < 15 years of age with conditional (170 to < 200 cm/sec) TCD flow velocity.		

Objectives	 Reversion of TCD category from conditional to normal
(cont'd)	 Proportion of participants with TCD response
	Change in hemoglobin (Hb) over time
	 Change in clinical measures of hemolysis
	 Annualized incidence rate of vaso-occlusive crises (VOCs)
	CCI
s	Safeta Obiantinan
	Safety Objectives: The safety objective is to assess the safety and tolerability of voxelotor compared to
	placebo.
	Pharmacokinetic Objectives:
	The pharmacokinetic (PK) objective is to assess the PK of voxelotor as evaluated by
	population pharmacokinetics (PPK) analysis.
Study Design	The study will be conducted globally at approximately 50 clinical sites.
	The study consists of 3 periods:
	 Screening: up to 35 days prior to randomization
	Treatment: 96 weeks
	 Follow-Up: 28 days (4 weeks) after the last dose
	Approximately 224 participants aged 2 to < 15 years will be randomized 1:1 to voxelotor or placebo.
	Participants ≥ 12 years old will be administered a fixed dose of voxelotor
	1500 mg/day. Participants younger than 12 years of age will receive voxelotor at a weight-based (1500 mg-equivalent) dose.
	Following completion of study treatment, eligible participants will be given the
	option to enroll in an open-label extension study (under a separate protocol) to
	receive voxelotor for a minimum of 3 years (3 years or until commercial product becomes available or a managed access program, whichever is longer).
	At the time of randomization, participants will be stratified by hydroxyurea (HU) use
	(yes/no), age (2 to ≤ 8 years; > 8 to < 15 years), Screening TCD flow velocity value
	(170 to < 185 cm/sec; 185 to < 200 cm/sec) and geographic region (Africa including
	Middle East and North Africa [MENA]; rest of world). Stratification of participants by age was chosen to evenly balance by age distribution using the expected median
	age of 8 years.
	10 36 37 m 47 80 38 5

	Dosing of participants between 2 and < 4 years of age:
	At least 15 participants from 2 to < 4 years of age will be enrolled. Enrollment of participants < 4 years of age will be initiated after the Data and Safety Monitoring Board (DSMB) has reviewed safety and PK data from at least 12 participants < 30 kg treated with voxelotor for at least 28 days. These data for at least 12 participants may be generated from any voxelotor clinical studies.
Duration of Study Participation	The duration of study involvement for an individual participant is expected to be approximately 105 weeks. The study will end when the last participant's last visit occurs.
Statistical Methods	Primary Endpoint The primary efficacy endpoint is the change from Baseline at 24 weeks in TAMMV arterial cerebral blood flow, as measured by TCD. Secondary Endpoints The secondary efficacy endpoints are as follows: • Change from Baseline in TCD flow velocity at Week 48 and Week 96 • Time to conversion to abnormal TCD flow velocity (≥ 200 cm/sec) • Time to reversion to normal TCD flow velocity (< 170 cm/sec)

	Pharmacokinetic Endpoint
	The endpoint is whole blood and plasma voxelotor PK as evaluated by PPK analysis using nonlinear mixed effects modeling.
	Sample Size
Statistical Methods (cont'd)	The sample size is planned to provide sufficient statistical power for the primary efficacy analysis and for a robust safety database. In addition, the number of events required to assess secondary efficacy endpoints, eg, percentage conversion to abnormal TCD category, is also considered.
	For the primary endpoint (change from Baseline in TCD flow velocity [cm/sec]), assuming equal allocation across treatment groups and a common variance, an estimate of the number of participants in each of 2 treatment groups used the following assumptions in the power calculation:
	 Targeted treatment effect: difference in mean change from Baseline in TCD flow velocity is 15 cm/sec
	 Common standard deviation is 24 cm/sec
	 A significance level of 5% (2-sided)
	Assuming a 20% drop out rate, a sample size of 112 participants per group provides > 95% power to detect the targeted treatment effect for the following hypothesis test using a Student's t-test:
	H ₀ : $\mu_1 = \mu_2$ versus H _A : $\mu_1 \neq \mu_2$
	where μ_1 and μ_2 stand for mean change from Baseline in TCD flow velocity at Week 24 in voxelotor and placebo groups, respectively.
	For the secondary efficacy endpoint of time to conversion to abnormal TCD category, assuming 35% of participant in the placebo group have experienced a TCD flow velocity > 200 cm/sec by Week 96, a hazard ratio of 0.5 between voxelotor group and placebo, a fixed follow up time of up to 96 weeks for each participant, and an overall 20% drop out rate, a total of 49 events is expected. This provides approximately 65% power for a log-rank test at a two-sided significance level of 5% and approximately 75% power at a two-sided significance level of 10% (PASS version 11).
	Efficacy Analyses
	The primary analysis of change in TCD flow velocity from Baseline to Week 24 will be performed using a mixed model for repeated measures (MMRM). Independent variables will include treatment, study visit, treatment by study visit interaction, and randomization stratification factors (ie, HU use, age, Screening TCD flow velocity, and geographic region). Within-subject variability will be modeled using an unstructured covariance matrix.
	The secondary endpoints will be analyzed as described below.
	Change from Baseline endpoints:
	 Change in TCD flow velocity from Baseline to Week 48 and Week 96 will be analyzed with the same MMRM as described for the primary efficacy endpoint (ie, change from Baseline in TCD flow velocity at Week 24). A single model will be fit incorporating data from all timepoints.
	 Change in Hb and clinical measures of hemolysis (unconjugated bilirubin, % reticulocytes, absolute reticulocyte, and LDH) from Baseline at Week 24, Week 48, and Week 96 will be analyzed with a similar approach.

	TCD responder endpoint:
Statistical Methods (cont'd)	 The TCD responder endpoint, defined as a TCD flow velocity reduction from Baseline ≥ 15 cm/sec at a given timepoint, eg, Week 24, Week 48, or Week 96, will be analyzed using an exact Cochran-Mantel-Haenszel (CMH) general association test stratified by the randomization stratification factors for the treatment difference between voxelotor and placebo.
	 Time to events endpoints:
	 For time to conversion from conditional to abnormal TCD, the Kaplan- Meier method will be used to estimate the landmark rates and the associated 95% confidence intervals in the voxelotor and placebo groups at Week 24, Week 48, and Week 96. A log-rank test stratified for the randomization stratification factors will be used to test the difference between voxelotor and placebo groups. A Cox proportional hazard model may be used to estimate the hazard ratio, as appropriate.
	 Time to reversion from conditional to normal TCD will be analyzed using a similar approach.
	Safety and Tolerability Analyses
	Safety analysis will be performed on all participants receiving at least one dose of study drug.
	Adverse events (AEs) will be classified according to the Medical Dictionary for Regulatory Activities (MedDRA). The incidence of treatment-emergent adverse events (TEAEs), defined as an event that occurs on or after Day 1 of study treatment or the worsening of a preexisting condition on or after Day 1 of study treatment, will be tabulated by System Organ Class (SOC), preferred term, severity, and relationship to study drug. Changes in laboratory parameters (hematology, serum chemistry, and liver function tests) and vital signs (eg, blood pressure [BP], pulse, and body temperature) over time will be summarized descriptively.
	SCD-related AEs will be collected and summarized separately (including VOC, acute chest syndrome, osteonecrosis, priapism, etc.)
	Pharmacokinetic Analyses
	 PPK analysis will consist of all participants who receive active study drug and have at least one measured concentration at a scheduled PK time point after the start of dosing. If any participants are found to be noncompliant with respect to dosing or have incomplete data, protocol deviations, or clinical events that affect PK, a decision will be made on a case-by-case basis as to their inclusion in the analysis. Participants in this population will be used for all PK summaries. PPK analyses using nonlinear mixed effects modeling will be performed to characterize voxelotor PK in plasma and whole blood. The influence of demographic covariates (such as body weight, height, age, gender) on voxelotor PK parameters (ie, clearance [CL] and volume of distribution) will be investigated. If appropriate, the voxelotor PK data may be pooled with PK data from other studies. Continuous variables will be descriptively summarized using mean, standard
	deviation (SD), coefficient of variation (CV%, as appropriate), median, minimum, maximum, and as appropriate, geometric mean. Categorical variables will be descriptively summarized by presenting the number (frequency) and percentage in each category.

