6.12.2. Serum Chemistry

Chemistry assessments include the following:

- ALT
- Albumin
- Alkaline phosphatase (ALK)
- Aspartate aminotransferase (AST)
- Bicarbonate
- Blood urea nitrogen (BUN)
- Chloride
- Calcium
- Creatinine
- Glucose
- LDH
- Sodium
- Potassium
- Bilirubin (total, direct and indirect)

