APPENDIX A. SCHEDULE OF ASSESSMENTS: SCREENING

Procedure	Screening Up to 35 Days Before Dosing
Informed Consent and Assent, as appropriate	X
Medical History	Х
Full Physical Examination	X
Blood Pressure a	X
Pulse Rate a	x
Body Temperature ^a	X
Body Weight	Х
Height	X
ECG (12-lead) b	X
Urinalysis	X
Serum Pregnancy Test (females, post menarche)	X
Hematology ^c	Х
Serum Chemistry ^d	Х
Fetal Hemoglobin	Х
Hemoglobin A	Х
Hemoglobin Genotype (if not already available) ^e	х
Malaria Test (performed at local laboratory) ONLY if there is clinical suspicion of active malaria infection ^f	Х
Hepatitis and HIV Serology - only if clinically indicated	X
Iron Studies (ferritin, transferrin, and serum iron)	X
Transcranial Doppler (2 sonograms performed per TCD Manual)	X
Concomitant Medications	Х
Adverse Events	x

Abbreviations: ECG, electrocardiogram; HIV, human immunodeficiency virus; TCD, transcranial Doppler.

^a Vital signs (blood pressure, pulse rate, body temperature) will be measured after a participant has rested for at least 5 minutes in the supine or recumbent position, as age appropriate and feasible. A repeated measurement of any of the vital sign parameters will be taken within 5 minutes if the first reading is outside the normal range and deemed clinically significant. ^b ECG (12 head) will be recorded in the average appropriate after a fract sector.

^b ECG (12-lead) will be recorded in the supine position after at least 5 minutes of rest.

^c Hematology assessments include the following: red blood cells; hematocrit; hemoglobin; platelets; white blood cells with differential (basophils, eosinophils, neutrophils, monocytes, and lymphocytes); % and absolute reticulocytes; red blood cell distribution width; mean corpuscular volume; mean corpuscular hemoglobin concentration; hemoglobin A (Screening only); alpha thalassemia and haplotype (Week 8 Only).

^d Chemistry assessments include the following: alanine aminotransferase; albumin; alkaline phosphatase; aspartate aminotransferase; bicarbonate; blood urea nitrogen; chloride; calcium; creatinine; glucose; lactate dehydrogenase; sodium; potassium; bilirubin (total, direct and indirect).

^e Hemoglobin genotype can be based on previously documented medical records, ie, previous laboratory tests.

^f Further tests will be conducted per the Investigator's discretion, at any point through the rest of the study, if there is a clinical suspicion of malarial infection.

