In the majority of DILI cases, elevations in AST (aspartate transaminase) and/or ALT (alanine transaminase) precede total bilirubin elevations (> 2 × ULN) by several days or weeks. The increase in total bilirubin typically occurs while AST/ALT is/are still elevated above 3 × ULN (ie, AST/ALT and total bilirubin values will be elevated within the same laboratory sample). In rare instances, by the time total bilirubin elevations are detected, AST/ALT values might have decreased. This occurrence is still regarded as a potential DILI. Therefore, abnormal elevations in either AST OR ALT in addition to total bilirubin that meet the criteria outlined below are considered potential DILI (assessed per Hy's law criteria) cases and should always be considered important medical events, even before all other possible causes of liver injury have been excluded.

The threshold of laboratory abnormalities for a potential DILI case depends on the participant's individual baseline values and underlying conditions. Participants who present with the following laboratory abnormalities should be evaluated further as potential DILI (Hy's law) cases to definitively determine the etiology of the abnormal laboratory values:

- Participants with AST/ALT and total bilirubin values within the normal range who subsequently present with AST or ALT values ≥ 3 × ULN AND a total bilirubin value ≥ 2 × ULN with no evidence of hemolysis and an alkaline phosphatase value < 2 × ULN or not available.
- For participants with baseline AST OR ALT OR total bilirubin values above the ULN, the following threshold values are used in the definition mentioned above, as needed, depending on which values are above the ULN at baseline:

- Preexisting AST or ALT baseline values above the normal range: AST or ALT values ≥ 2 times the baseline values AND ≥ 3 × ULN; or ≥ 8 × ULN (whichever is smaller).
- Preexisting values of total bilirubin above the normal range: total bilirubin level increased from baseline value by an amount of ≥ 1 × ULN or if the value reaches ≥ 3 × ULN (whichever is smaller).

Rises in AST/ALT and total bilirubin separated by more than a few weeks should be assessed individually based on clinical judgment; any case where uncertainty remains as to whether it represents a potential Hy's law case should be reviewed with the sponsor.

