8.3.4. Clinical Laboratory Assessments

All hematology and chemistry laboratory assessments will be performed by a central laboratory. Laboratory data will be converted into System International (SI) units for data analysis.

090177e1a2bf4d41Approved\Approved On: 31-Jan-2025 17:16 (GMT)

The following protocol-specified clinical laboratory findings will be summarized using descriptive statistics by treatment group:

1. Hematology:

- RBCs
- Hematocrit
- Platelets
- White blood cells (WBCs) with differential (basophils, eosinophils, neutrophils, monocytes, and lymphocytes)
- RBC distribution width (RDW)
- Mean corpuscular volume (MCV)
- Mean corpuscular hemoglobin concentration (MCHC)

2. Chemistry:

- Alanine aminotransferase (ALT)
- Albumin
- Aspartate aminotransferase (AST)
- Blood urea nitrogen (BUN)
- Calcium
- Creatinine
- Glucose
- LDH
- Bilirubin (total and direct)

Note: Planned summaries of change from baseline in hemoglobin and clinical measures of hemolysis (indirect bilirubin, % reticulocytes, absolute reticulocytes, and LDH) are described in Section 8.2.3.

Descriptive statistics will be presented for baseline, each evaluation post baseline, and change from baseline for each post baseline evaluation. If any of the clinical laboratory assessments are below the lower limit of quantitation or above the upper limit of quantitation, then the numerical limit will be used in the tabulation of the descriptive statistics.

Laboratory abnormalities will be graded via the Common Terminology Criteria for Adverse Event (CTCAE) using the current version at the time of analysis database lock. The number and percentage of subjects experiencing treatment-emergent graded abnormalities will be summarized by treatment group. Laboratory abnormality shifts from baseline through Week 24, Week 48, and Week 96 will be summarized by treatment group.

090177e1a2bf4d41Approved\Approved On: 31-Jan-2025 17:16 (GMT)

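### SAP 8.3.4 leaves 5 of the protocol's 14 chemistry tests, including alkaline phosphatase, out of the by-arm change-from-baseline summaries and gives no reason

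*Protocol*

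**What the plan says.** The synopsis (Safety and Tolerability Analyses) and Protocol 8.5 use the same wording, "Changes in laboratory parameters (hematology, serum chemistry, and liver function tests", for what will be summarized descriptively over time, alongside vital signs.

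Protocol 6.12.2 sets out the chemistry panel under "Chemistry assessments include the following". The panel has 14 entries, one of them "Alkaline phosphatase (ALK", and the chemistry footnote in Appendix A repeats it. Protocol 6.12 sends laboratory assessments to a central laboratory.

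SAP 8.3.4 opens its own list with "The following protocol-specified clinical laboratory findings will be summarized using descriptive statistics by treatment group". For the tests on that list it plans statistics at baseline, at each later evaluation, and for change from baseline. A Note sends hemoglobin and "clinical measures of hemolysis (indirect bilirubin, % reticulocytes, absolute reticulocytes, and LDH) are described in Section 8.2.3". Separately, the section says "The number and percentage of subjects experiencing treatment-emergent graded abnormalities will be summarized by treatment group", and it plans abnormality shifts by arm through Weeks 24, 48 and 96. SAP Section 2 gives the SAP precedence over the protocol where they differ.

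**The concern.** The SAP calls its list protocol-specified, yet the chemistry part is shorter than the protocol's panel. It is worded as a complete list, not as a set of examples. A programmer working from it would produce no table of level or change for the five absent tests, although the blood is drawn and assayed under the protocol.

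Clinical laboratory assessments are a named safety endpoint (Protocol 8.1.4, SAP 4.4), and the safety objective is a comparison with placebo. At stake is whether a drift in one arm that stays below a grading threshold would appear in any planned table. Alkaline phosphatase matters most of the five. Protocol Appendix D uses it, with AST, ALT and total bilirubin, to define a potential drug-induced liver injury case: "an alkaline phosphatase value < 2 × ULN or not available".

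**Working it through.** The plan states no count to reproduce, so the check is an item-by-item comparison of the lists.

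**Chemistry**

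- Protocol 6.12.2 (14): ALT, albumin, alkaline phosphatase, AST, bicarbonate, BUN, chloride, calcium, creatinine, glucose, LDH, sodium, potassium, bilirubin.
- SAP 8.3.4 (9): ALT, albumin, AST, BUN, calcium, creatinine, glucose, LDH, bilirubin.
- Difference: 14 − 9 = 5, namely alkaline phosphatase, bicarbonate, chloride, sodium and potassium. 5/14 = 36%. Nothing on the SAP list lies outside the protocol panel.

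**Does the way bilirubin is counted matter?** The protocol names total, direct and indirect. Counted separately, the protocol has 14 + 2 = 16 entries. SAP 8.3.4 has 9 + 1 = 10 (total and direct), and indirect bilirubin in SAP 8.2.3 makes 11. 16 − 11 = 5, the same five tests, or 5/16 = 31%.

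**Are the five handled elsewhere in the SAP?** Hematology shows how the SAP treats items it takes off the list. Of the serial hematology items in Protocol 6.12.1 (RBC, hematocrit, hemoglobin, platelets, WBC with differential, reticulocytes, RDW, MCV, MCHC), SAP 8.3.4 lists seven of nine. The two left off, hemoglobin and reticulocytes, are covered by the Note pointing to SAP 8.2.3. Hematology is therefore fully accounted for. The five chemistry tests have no such pointer. Avoiding duplication does not explain the gap either, because LDH is both on the list and in the Note.

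**Do the other tables in SAP 8.3.4 fill the gap?** The sentences on graded abnormalities and shifts are not limited to the nine listed tests, so they may cover some or all of the five. They do not name their analytes. A table of grades registers a participant who crosses a threshold. It does not give the change over time that Protocol 8.5 describes.

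**Liver definition.** Appendix D uses four analytes: AST, ALT, total bilirubin and alkaline phosphatase. SAP 8.3.4 summarizes three of the four by arm, and alkaline phosphatase is the one left out.

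**After the fix.** 9 + 5 = 14 of 14 panel tests would be summarized.

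**The case against.** The strongest case against the point has four parts.

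First, the protocol promises summaries by class of test, not by analyte, and the SAP covers tests in every class, including ALT, AST, albumin and bilirubin. Narrowing a general commitment is ordinary SAP work. This is fair, and it makes the conflict softer than a broken promise for each test. But the protocol itself defines the chemistry panel, the SAP describes its list as protocol-specified, and no reason for the narrowing is given.

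Second, a reader might infer that these five tests cannot be compared between arms at all. The documents do not support that. SAP 8.3.4 plans graded and shift tables by treatment group in general wording. Clinically significant abnormalities are recorded as adverse events (Protocol 6.12 and 7.2.3) and reach the by-arm tables of SAP 8.3.3. What is missing is the summary of level and change, together with a stated scope for the graded and shift tables.

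Third, liver cases are judged participant by participant. The Appendix D definition allows for a missing alkaline phosphatase value, and potential cases are reported as serious adverse events. This stands: case finding does not depend on a table of group means. The case for including alkaline phosphatase is that the group picture should be complete.

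Fourth, the table mock-ups are in a separate document (SAP Section 12) and may already include the tests, and SAP Section 10 allows further analyses in the study report if they are identified. Both are true. Neither puts the five tests in the plan as written.

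**Conclusion.** The gap is real and modest. SAP 8.3.4 plans no by-arm descriptive or change-from-baseline summary for 5 of 14 protocol chemistry tests (36%), gives no reason, and does not say which analytes its graded and shift tables cover. No efficacy result, visit or sample is affected. It is a safety-reporting correction worth making because it is cheap.

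This rests on two assumptions: that the SAP 8.3.4 list is meant to be complete, as its wording suggests, and that the unseen table mock-ups follow it.

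Two further inferences should be resisted. A reader might suppose that the tests were removed in a later SAP version without being logged. The SAP's summary of changes records only differences between versions, and the short list may date from version 1.0, in which case there was nothing to log. A reader might also connect the omission with the safety imbalance behind the May 2024 dose pause. SAP Section 2 does not describe that imbalance, and nothing ties it to liver tests or electrolytes.

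**What to change.** In SAP 8.3.4, add alkaline phosphatase, sodium, potassium, chloride and bicarbonate to the chemistry list, so that baseline, each visit and change from baseline are summarized by treatment group. In the same section, state that the graded-abnormality and shift tables cover every Protocol 6.12.2 chemistry test that has a grading scale. If the sponsor means to leave any test out, the SAP should say which one and why.

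The cost is SAP wording and five more analytes in existing table shells, so the safety tables become slightly longer. The tests already belong to the protocol's central-laboratory panel, so no new sample, visit or participant is needed. SAP 6.3 describes the final study analysis as still to come, so on the documents the additional summaries can be included there.
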